APPENDIX A – CLINICAL EVALUATIONS

Clinical Evaluation	Illumination	Testing	Group	Preop	Op*	Day 1**	Wk 1**	Mon 1**	Mon 3	Mon 6	Mon 12
Ocular & Health History	N/A	N/A	Both	Х		Х	Х	Х	Х	Х	Х
Cover Test	N/A	N/A	Both	Х							
Sighting Eye Dominance	N/A	N/A	Both	Х					Х		
Pupil Size	Photopic Mesopic Dilated	Monocular (OD & OS) Monocular (OD & OS) Monocular (OD & OS)	Both	X X X					X X X ^A	X X	X X X
Swinging Flash Light Test	N/A	Monocular (OD & OS)	Both	Х					Х		
Biometry Measurements	N/A	Monocular (OD & OS)	Both	Х							
Corneal Topography	N/A	Monocular (OD & OS)	Both	Х						Х	Х
Uncorrected Distance Visual Acuity (UCDVA)	Photopic	Monocular (OD & OS) Binocular (OU)	Both	X X		М	М	М	M M	M M	M M
Uncorrected Intermediate Visual Acuity (UCIVA)	Photopic	Monocular (OD & OS) Binocular (OU)	Both						M M	M M	M M
Uncorrected Near Visual Acuity (UCNVA)	Photopic	Monocular (OD & OS) Binocular (OU)	Both	X X					M M	M M	M M
Manifest Refraction	Photopic	Monocular (OD & OS)	Both	Х			М	М	М	М	М
Add (Near)	Photopic	Monocular (OD & OS)	Both							М	
Distance-Corrected Distance Visual Acuity (DCDVA)	Photopic	Monocular (OD & OS) Binocular (OU)	Both	Х			М	М	M M	M M	M M
Distance-Corrected Intermediate Visual Acuity (DCIVA)	Photopic	Monocular (OD & OS) Binocular (OU)	Both						M M	M M	M M
Distance-Corrected Near Visual Acuity (DCNVA)	Photopic	Monocular (OD & OS) Binocular (OU)	Both						M M	M M	M M
Defocus Curve Test	Photopic	Monocular (OD & OS) Binocular (OU)	Both						M M		
AcuFocus, Inc. - Confidential

Clinical Evaluation	Illumination	Testing	Group	Preop	Op*	Day 1**	Wk 1**	Mon 1**	Mon 3	Mon 6	Mon 12
+0.75 D Distance Corrected Distance Visual Acuity (+0.75 DCDVA)	Photopic	Monocular (2 nd eye) Binocular (OU)	Both							M M	
+0.75 D Distance Corrected Intermediate Visual Acuity (+0.75 DCIVA)	Photopic	Monocular (2 nd eye) Binocular (OU)	Both							M M	
+0.75 D Distance Corrected Near Visual Acuity (+0.75 DCNVA)	Photopic	Monocular (2 nd eye) Binocular (OU)	Both							M M	
Near Stereoacuity (w/ UCNVA; & w/ DCNVA with Add)	Photopic	Binocular	Both							Х	
Slit-Lamp Exam (SLE)	N/A	Monocular (OD & OS)	Both	Х		Х	Х	Х	Х	Х	Х
IOL Centration & Tilt w/ SLE	N/A	Monocular (OD & OS)	Both			Х	Х	Х	Х	Х	Х
Toric IOL axis w/ SLE	N/A	Monocular (OD & OS)	Both			X	x ^c				
TBUT	N/A	Monocular (OD & OS)	Both	Х					Х	Х	Х
Corneal Staining	N/A	Monocular (1 st eye) Monocular (2 nd eye)	Both	X X			Х	X ^D	X X	X X	X X
Intraocular Pressure	N/A	Monocular (OD & OS)	Both	Х		Х	Х	Х	Х	Х	Х
Gonioscopy	N/A	Monocular (OD & OS)	Both	Х						Х	
Dilated Fundus Exam (BIO)	N/A	Monocular (OD & OS)	Both	Х							Х
Dilated Slit-lamp Exam	N/A	Monocular (OD & OS)	Both	Х							Х
Dilated Ocular Coherence Tomography (OCT)	N/A	Monocular (OD & OS)	Both	Х							
Patient Reported Outcome Questionnaire(s)	N/A	N/A	Both	X					X	X	X
Non-directed Question	N/A	N/A	Both	X		Х	Х	Х	Х	Х	Х

Clinical Evaluation	Illumination	Testing	Group	Preop	Op*	Day 1**	Wk 1**	Mon 1**	Mon 3	Mon 6	Mon 12
CONTR	AST SENSITIVI	TY SUBGROUP ONLY -	CONTRAS	T SENSITI	VITY A	ND LOW	CONTR	AST ACUI	TY TEST	ING	
Distance Contrast Sensitivity (w/ glare & w/o glare)	Photopic Mesopic	Monocular (OD & OS) Binocular (OU)	Both							M ^A M ^A	M ^B M ^B
10% contrast UCDVA	Photopic	Monocular (2 nd eye) Binocular (OU)	Both							M ^A M ^A	M ^B M ^B
10% contrast UCIVA	Photopic	Monocular (2 nd eye) Binocular (OU)	Both							M ^A M ^A	M ^B M ^B
10% contrast UCNVA	Photopic	Monocular (2 nd eye) Binocular (OU)	Both							M ^A M ^A	M ^B M ^B
10% contrast DCDVA	Photopic	Monocular (2 nd eye) Binocular (OU)	Both							M ^A M ^A	M ^B M ^B
10% contrast DCIVA	Photopic	Monocular (2 nd eye) Binocular (OU)	Both							M ^A M ^A	M ^B M ^B
10% contrast DCNVA	Photopic	Monocular (2 nd eye) Binocular (OU)	Both							M ^A M ^A	M ^B M ^B
RETIN	RETINAL DIAGNOSTIC TESTING SUBGROUP ONLY – SUBGROUP-SPECIFIC RETINAL DIAGNOSTIC TESTING										
Undilated Threshold Visual Field Testing (Central 30-2)	Photopic	Monocular (OD & OS)	Test	X^A					X^A		
Dilated Ocular Coherence Tomography (OCT) Images	N/A	Monocular (OD & OS)	Test	X^A					X^A		
Dilated Fundus Photography	N/A	Monocular (OD & OS)	Test	X ^A					X^A		
* Op (operative) visits are repeated for each eye's surgery and the associated tests are performed on that operated eye only.											

** Day 1, Week 1 and Month 1 visits are repeated after each eye's surgery and the associated tests are performed on that operated eye only.
 ** Day 1, Week 1 and Month 1 visits are repeated after each eye's surgery and the associated tests are performed on the most recently operated eye only.
 ^A Subgroup testing only. Group sizes are specified in the statistical analysis plan.
 ^B Repeated at the 12-month visit for those subjects that have had a posterior capsulotomy procedure after the 6-month visit.
 ^C Repeated at postop visits if medically indicated as determined by investigator.

^D Repeated at 1 month visit if needed. X = tests to be performed by non-masked examiner; M = tests to be performed by masked examiner.

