1.0 SYNOPSIS	
PROTOCOL TITLE:	Clinical Evaluation of a Small Aperture Extended Depth of Focus Intraocular Lens
	Protocol Number: SAIL-101-UNI
TREATMENTS:	Investigational Study Lens : Unilateral implantation of the IC-8 [®] intraocular lens (IOL), a small aperture extended depth of focus hydrophobic acrylic intraocular lens, implanted in conjunction with an approved AcrySof [®] IQ or TECNIS [®] aspheric monofocal (SA60WF or ZCB00) or monofocal toric (SA6AT3, SA6AT4, ZCT150 or ZCT225) IOL in the fellow eye.
	Control Monofocal or Monofocal Toric Study Lens : Bilateral AcrySof IQ or TECNIS aspheric monofocal (SA60WF or ZCB00) or monofocal toric (SA6AT3, SA6AT4, ZCT150 or ZCT225) IOL.
CLINICAL HYPOTHESIS:	The IC-8 IOL, when implanted in conjunction with a monofocal IOL in the fellow eye, will demonstrate better binocular intermediate and near visual acuity compared to bilateral aspheric monofocal IOLs. The IC-8 IOL will demonstrate extended depth of focus compared to the monofocal IOL. Additionally, the IC-8 IOL will tolerate preoperative corneal astigmatism up to 1.50 D better than bilateral monofocal IOL implantation.
OBJECTIVE:	The objective of this study is to determine the safety and effectiveness of the IC-8 IOL implanted in one eye and a monofocal IOL implanted in the fellow eye, in accordance with the indication.
OVERALL STUDY DESIGN:	
Structure:	Prospective, multi-center, open-label, parallel-group, non-randomized, examiner-masked, one-year clinical study. The binocular performance of the subjects in the test group implanted with the IC-8 IOL will be compared to the binocular performance of the subjects in the control group implanted with monofocal IOLs. The monocular performance of the eyes implanted with the IC-8 IOL will be compared to the monocular performance of the fellow

	control eyes implanted with the monofocal IOL in subjects from the test group.
Number of sites:	Approximately 18 to 25 investigational U.S. sites
Study Duration:	One year with a possibility of two additional years for post-approval data.

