In order for the subject to complete the enrollment in the study, the first implanted eye in both the test and control groups must achieve the qualification criteria of 20/32 or better UCDVA and 20/25 or better BCDVA (or Snellen equivalent), have no ongoing ocular adverse events, and have normal corneal health as assessed by slit lamp biomicroscopy (Grade 1+ or less edema and Grade 1 or less SPK). The subject must qualify within the 1-week to 1-month visit windows (7 to 45 days from the 1st eye surgery). The subject will complete study enrollment and will receive the investigational device in the second eye (test group) or monofocal or monofocal toric IOL in the second eye (control group). Postoperative evaluations will be scheduled at 1 Day, 1 Week, 1, 3, 6, and 12 Months after the second eye surgery.

If the first implanted eye does not achieve the visual acuity and corneal health criteria within 7 to 45 days from the 1st eye surgery, the subject will be disqualified and exited from the study and will not be included in the study cohort or analysis population. This would ensure that the subject is not needlessly exposed to the risk of the investigational device when the safety and effectiveness of the investigational device is to be determined.

In general, the principal investigator/sub-investigator will perform the initial assessment and preoperative and postoperative procedures (with the exception of study-specific visual acuity testing, refraction, defocus testing and contrast measurements) and perform all eye surgeries in the study. To maintain consistency, a single individual examiner (e.g., study technician designated by the investigator) should conduct all study-specific visual acuity and refraction measurements. A back-up examiner should also be designated and trained. Additionally, the examiner (and back-up) will be masked to the treatment received by the subjects under examination.

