DCIVA	-0.25 D added to Manifest Refraction
DCNVA	-0.25 D added to Manifest Refraction
+0.75 DCDVA	+0.75 D added to Manifest Refraction
+0.75 DCIVA	+0.50 D added to Manifest Refraction
+0.75 DCNVA	+0.50 D added to Manifest Refraction
10% contrast UCDVA	+0.25 D
10% contrast UCIVA	None
10% contrast UCNVA	None
10% contrast DCDVA	Manifest Refraction
10% contrast DCIVA	-0.25 D added to Manifest Refraction
10% contrast DCNVA	-0.25 D added to Manifest Refraction

 Table 7: Infinity-Adjusted Refraction by Vision Test

Near Stereoacuity:

Near stereoacuity testing will be performed binocularly at the 6-month visit using the Randot stereo test (circles test) once in the uncorrected near condition and once in the distance corrected near condition, the infinity-adjusted refraction will be used for the testing, i.e., -0.25 D added to manifest refraction.

Defocus Curves:

Defocus curves will be performed monocularly and binocularly using ETDRS charts in the CTS calibrated for 4-meter test distance in standard photopic conditions, with the best-corrected distance manifest refraction. A defocus curve should be obtained by using the manifest refraction and measuring the visual acuity between +2.00 D and -5.00 D in 0.5 D defocus steps, except in the region from +0.50 D through -0.50 D, which should be done in 0.25 D steps.¹⁷ Defocus curve

testing will be performed at the 3-month postoperative visit (refractive stability is expected to be achieved by the 3-month visit). No infinity adjustment to manifest refraction is needed for defocus curve testing. Instructions for performing defocus curve testing using the CTS are provided in **Appendix H**.

Contrast Sensitivity Testing (subgroup testing):

Contrast sensitivity under photopic and mesopic conditions will be measured at the 6-month postoperative visit (and repeated at the 12-month visit for those subjects that have had a posterior capsulotomy procedure after the 6-month visit) in a contrast sensitivity subgroup using the sine wave gratings in the CTS. Instructions for performing contrast sensitivity testing with using the CTS are provided in **Appendix I.** A minimum of 177 test subjects and 59 control subjects are needed in the contrast sensitivity subgroup as determined in the SAP. To achieve this sample size at the time of testing, approximately 12-15 sites will be included in the contrast sensitivity subgroup.

Pupil Size:

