10.3. POTENTIAL RISKS WITH INVESTIGATIONAL DEVICE

The following are potential risks associated with the investigational device or the implantation procedure:

- Night vision problems
- Dimness in vision
- Negative dysphotopsia
- Glare, halos, starbursts, loss of contrast sensitivity

- Difficulty with depth perception, Pulfrich effect
- Double vision, ghosting, blurry vision, fluctuating vision, hazy vision, difficulty focusing
- Obstructed vision
- Surgically induced astigmatism > 2D
- Difficulty with retinal diagnostic evaluation and/or performing retinal treatment
- Risk of laser treatments (possible damage can occur to the IC-8 IOL mask while performing photodynamic laser or any other ocular laser procedure)

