18.0 DATA ANALYSIS METHODS

This section (section 18.0 through 18.4) highlights the key statistical methods and analyses planned for this study. The SAP includes details for all statistical methods, plans, adverse events reporting methods, and sample size calculations for the study.

Some key data and analysis conventions include the following:

For the primary and secondary effectiveness endpoints, the six-month postoperative visit will be the primary analysis time point unless otherwise noted. For the primary safety endpoints, the 12-month study visit will be the primary analysis time point.

Binocular safety and effectiveness analyses will compare the test group and the control group. Monocular safety and effectiveness analyses will compare the IC-8 IOL eyes and the monofocal fellow eyes within the test group. All co-primary effectiveness and safety endpoints have to be met to claim overall effectiveness and safety success. There is one secondary effectiveness endpoint regarding the tolerance to astigmatism in IC-8 IOL eyes, and this endpoint will only be tested when all co-primary effectiveness endpoints have been achieved. Under this plan, type I error rates will be controlled at a significance level of 0.05 per individual hypothesis without adjustment for multiplicity under any family. Other statistical comparisons in the additional analyses and supportive analyses should not be used for the purpose of claims.

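### Month 6 near stereoacuity goes to a non-masked examiner, while every other postoperative examiner-measured vision-performance test done in both groups is masked

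*Combined protocol and SAP*

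**What the plan says.** The Synopsis describes the trial as a "Prospective, multi-center, open-label, parallel-group, non-randomized, examiner-masked, one-year clinical study".

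Section 9.1 has the principal investigator or a sub-investigator generally carry out the pre- and postoperative procedures, "with the exception of study-specific visual acuity testing, refraction, defocus testing and contrast measurements". The same people perform all the surgeries. A designated examiner does the acuity and refraction measurements, and "the examiner (and back-up) will be masked to the treatment received by the subjects under examination".

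On the test itself, Section 9.7 states: "Near stereoacuity testing will be performed binocularly at the 6-month visit using the Randot stereo test (circles test"), once uncorrected at near and once with distance correction. It does not say who performs the test. Appendix A does. The row "Near Stereoacuity (w/ UCNVA; & w/ DCNVA with Add") is binocular, covers both groups, and carries a single X at Month 6. The legend reads: "X = tests to be performed by non-masked examiner; M = tests to be performed by masked examiner".

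Section 10.3 lists "Difficulty with depth perception, Pulfrich effect" among the potential risks of the device or procedure. Section 18.0 gives the general analysis rule: "Binocular safety and effectiveness analyses will compare the test group and the control group".

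**The concern.** Subjects know their lenses and were not randomised, so examiner masking is the design's main protection against measurement bias. Appendix A applies it to acuity, refraction, defocus and contrast, but not to stereoacuity.

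Stereopsis is a binocular function, and the test arm has a small-aperture lens in one eye only. Depth perception is therefore an obvious safety question for this device. If the person giving the test knows the group, differences in encouragement, in time allowed or in how doubtful responses are accepted could enter the test-versus-control difference. The documents do not describe how the Randot test is to be scored or prompted, so this is a general feature of response-based testing and not something the protocol shows to be happening.

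At stake is the credibility of one supportive safety result, whether it shows a deficit or reassures that there is none.

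**Working it through.** No formula or sample-size figure is involved. The check is a reading of every postoperative Appendix A row against the legend, classed by mark, by group and by type of test.

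**1. Vision-performance rows done in both groups and marked M**
- Uncorrected distance, intermediate and near acuity: 3
- Manifest refraction and near add: 2
- Distance-corrected distance, intermediate and near acuity: 3
- Defocus curve: 1
- +0.75 D distance-corrected acuity at three distances: 3
- Contrast sensitivity (subgroup): 1
- 10% contrast acuities (subgroup): 6

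Total: 3 + 2 + 3 + 1 + 3 + 1 + 6 = 19.

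**2. Vision-performance rows done in both groups and marked X**
- Near stereoacuity: 1

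**3. Other postoperative X rows, and why they are not counted**
- Visual field testing is X, but it is done in the test group's retinal subgroup only. Appendix E compares it with the preoperative visit and between eyes, not between groups.
- Sighting dominance is response-based and X in both groups. Section 9.1 uses it to stratify the data.
- The swinging flashlight test is X in both groups. It checks for a pupillary defect.
- Questionnaires and the open-ended question are patient-reported.
- The rest are history, pupil size, topography, slit-lamp findings, lens position, ocular surface, pressure, gonioscopy and fundus examination.

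**4. Is the X a stray mark?** It does not look like one. Section 9.1 leaves stereoacuity off its list of exceptions, which agrees with Appendix A. Read literally, the default tester is an investigator from the team that performs the surgery, although another non-masked member of staff would also fit the legend.

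**5. What else could protect the comparison?**
- A preoperative baseline: Appendix A has none for stereoacuity.
- A fellow-eye comparison, as Section 18.0 uses for monocular outcomes: not available for a binocular test.
- Automated capture: Section 13.1 sends acuity, contrast and defocus results from the computerised test system straight to the database. The Randot test is separate equipment (Appendix B) and is not among those results.

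Manifest refraction is also recorded by hand, and Section 13.1 gives that task to the masked examiner. Manual recording is therefore no reason to leave stereoacuity unmasked.

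**The case against.** The strongest reply is that the protocol is consistent with itself. Section 9.1 promises masking for named tasks, stereoacuity is not one of them, and Appendix A follows. That stands: this is a gap in coverage, not a contradiction or a broken commitment. The point is a recommendation to extend masking.

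Several stronger readings are tempting, and the documents do not support them:

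- **A named between-group stereoacuity analysis is planned.** Section 18 names none. A comparison follows only from the general rule in Section 18.0. Section 18.4 leaves other analyses to the SAP, and no separate SAP text was available for this review.
- **Stereoacuity is the only information collected on depth perception.** Sections 9.3 and 9.7 also provide two questionnaires, one covering driving tasks, together with an open-ended vision question. Adverse events are assessed at each visit. The questionnaire items are not reproduced, so one cannot say that none of them touches on depth.
- **The comparison will involve 300 test and 100 control subjects.** Those are one-year completion targets. The protocol gives no expected Month 6 count.
- **The trial's conclusions are at risk.** Stereoacuity is neither a primary nor a secondary endpoint, and Section 18.0 bars additional and supportive comparisons from use for claims.

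Two further limits are fair. Masking the examiner does not remove response bias from subjects who know their lenses. Also, the statement that stereoacuity is the one exception depends on counting examiner-measured performance outcomes and leaving out sighting dominance, which is response-based but used as a stratifier.

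A worry that this test would reveal the group to the masked examiner carries little weight, because that examiner already runs the defocus curve.

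**Conclusion.** The point holds as a minor, inexpensive improvement. Of 20 postoperative rows for examiner-measured vision performance in both groups, 19 are masked and one is not. The exception is the only examiner-administered stereopsis test shown for a listed device risk. With no baseline, no fellow-eye comparator and no randomisation, its interpretation rests on the control group and on even-handed testing.

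The possible bias touches one test under two correction conditions at one visit. Its size and direction are unknown and cannot be bounded from the documents. No success criterion changes.

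The conclusion assumes that the Section 18.0 rule applies to stereoacuity and that the SAP does not assign the test to a masked examiner.

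**What to change.** - In Appendix A, change the Month 6 near-stereoacuity entry from X to M.
- In Section 9.1, add stereoacuity to the tests excepted from the investigator, and state that the masked examiner or back-up performs it.

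The masked examiner already measures binocular uncorrected and distance-corrected near acuity and determines the near add at Month 6. The cost is a few extra minutes at that visit, with no new staff or equipment.

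While that row is open, the corrected test condition should be reconciled. Appendix A describes it as distance-corrected near acuity with an add. Section 9.7 describes manifest refraction adjusted by -0.25 D and mentions no add.

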APPENDIX B - EQUIPMENT LIST

The following equipment will be supplied to a study site for the duration of the study provided that the site does not already have such equipment available for use. This equipment loan will be documented in the clinical trial agreement. This equipment is to be returned to AcuFocus at the completion of the study.

- M&S CTS (including a laptop, a monitor, a tablet, glare source, mesopic filter, cart)
- Table for the CTS
- Glare source for CTS
- Randot Stereogram (if site does not have a Randot Stereogram)

Site should have the following to participate in the study:

- Corneal topographer
- Optical Coherence Tomographer

APPENDIX C - SLIT-LAMP EXAM RATINGS

The biomicroscopic slit-lamp exam should be performed by the same evaluator at each study visit. Adherence to the grading scales will improve consistency across study sites.

None	0	No opacification				
Mild	1+	Obscures 10% of intra-pupillary space				
Moderate	2+	Obscures 10 to 50% of intra-pupillary space				
Pronounced	3+	Obscures 50-90% of intra-pupillary space				
Severe	4+	Obscures 90% of intra-pupillary space				

A. CATARACT GRADING *

* Optometric Clinical Practice Guideline Care of The Adult Patient with Cataract (American Optometric Association- Reference Guide for Clinicians)

B. RATINGS OF AQUEOUS CELLS AND FLARE

The Standardization of Uveitis Nomenclature (SUN) grading scales are to be used to rate aqueous cells and flare.^{18,19}

The SUN Working Group Grading Scheme for Anterior Chamber Cells					
Grade	Cells in Field [†]				
0	<1				
0.5+	1-5				
1+	6-15				
2+	16-25				
3+	26-50				
4+	>50				
[†] Field size is a 1 mm by 1 mm slit beam					

CELLS

FLARE

The SUN Working Group Grading Scheme for Anterior Chamber Cells						
0	None					
1+	Faint					
2+	Moderate (iris and lens details clear)					
3+	Marked (iris and lens details hazy)					
4+	Intense (fibrin or plastic aqueous)					

C. RATINGS OF CORNEAL EDEMA

Corneal edema should be classified according to the haziness of the epithelium, the number of microcysts observed and the clouding of the stroma.

None	0	Normal transparency:
		a. No epithelial or sub-epithelial haziness
		b. No microcysts
		c. No stromal cloudiness
Trace	1+	a. Barely discernable localized epithelial or sub-epithelial haziness and/or
		b. 1 to 20 microcysts
		c. Barely discernable localized stromal cloudiness
Mild	2+	a. Faint but definite localized or generalized epithelial, sub-
		epithelial or stromal haziness/cloudiness, and/or
	_	b. 21-50 microcysts
Moderate	3+	a. Significant localized or generalized epithelial, sub-epithelial or
		stromal haziness/cloudiness, and/or
		b. 51-100 microcysts
Severe	4+	a. Significant widespread epithelial or stromal cloudiness, giving
		dull glass appearance to corneal or numerous coalescent bullae
		(note number and location of bullae), and/or
		b. >100 microcysts or bullae, and/or
		c. Numerous striae (note number and location of striae or folds)

D. POSTERIOR CAPSULE STRIAE GRADING SCALE

The following five-point grading scale is to be used for rating striae in the posterior capsule:

None	0	None
Trace	1+	One detectable, barely noticeable striae
Mild	2+	One or two prominent striae
Moderate	3 +	Three or more prominent striae, but visibility of retina is not impacted
Severe	4+	Three or more prominent striae affecting visualization of the retina

E. POSTERIOR CAPSULE OPACIFICATION GRADING SCALE

Below is the five-point grading scale to be used for PCO determination:

None	0	Normal posterior capsule with no area of opacity. Red reflex bright.
Trace	1+	Some loss of transparency involving the posterior capsule. Red reflex fairly bright.
Mild	2+	Mild loss of transparency with cloudiness extending through most of the posterior capsule. There may be a few Elschnig pearls in the posterior capsule. Red reflex mildly diminished.
Moderate	3+	Moderate loss of transparency with difficulty visualizing the retina. There may be multiple Elschnig pearls in the posterior capsule. Red reflex markedly diminished.
Severe	4+	Posterior capsule very opaque with inability to view the retina. The posterior capsule may have confluent Elschnig pearls and fibrous scarring. Red reflex barely visible.

